3.10.4 Documentation

At the time of study withdrawal or completion for any reason, the study exit CRF will be completed, including the reason for exit.

3.10.5 Continuing Medical Care

Subjects leaving the study at any time will continue to receive appropriate medical care without prejudice.

3.10.6 Lost to Follow-Up

If the investigator has attempted to contact a subject at least three times within 60 days and received no response, the subject may be considered lost to follow-up. The investigator will document that a minimum of three attempts were made to contact the subject, including sending a certified letter if current address is known, prior to exiting the subject from the study.

At the time of confirmed lost to follow-up status, the study exit CRF will be completed.

3.11 Procedures

3.11.1 Index Procedure

The investigator will confirm that the following have been achieved:

- For women of childbearing potential – a negative pregnancy test
- Baseline NIHSS score
- The patient is not on amiodarone

FARAPULSE Endocardial Ablation procedure patients will undergo anesthesia according to institutional protocol. They will then be prepared in conventional sterile fashion for a cardiac catheterization procedure. Femoral vein access will be obtained via Seldinger technique. Transseptal access to the left atrium will then be obtained using either a FARADRIVE Deflectable sheath or a commercially approved sheath and Brockenbrough needle. The transseptal sheath will then be withdrawn, leaving guidewire access to the left atrium. The FARADRIVE Deflectable Sheath, or a commercial equivalent as described above in **Table 2**, will then be prepared and advanced via guidewire to the left atrium. Commercially approved multielectrode pacing catheters will then be placed via conventional technique at the investigator's discretion. A baseline electrophysiological assessment of pulmonary vein connection to the left atrium will be made and documented via FARAWAVE or a commercially approved diagnostic catheter placed in each addressable pulmonary vein. A baseline 3D electroanatomical map may also be made at the investigator's discretion. The diagnostic catheter will then be removed from the FARADRIVE Deflectable Sheath or commercial equivalent.

The FARAWAVE Ablation Catheter will then be prepared and advanced over the guidewire to the left atrium through the sheath. The guidewire will be advanced into a target pulmonary vein, the catheter splines will be deployed to suit target anatomy by retracting the deployment knob, and the deployed catheter will be advanced to the ostium of the target pulmonary vein. At the investigator's discretion, contrast venography may be performed to verify placement of the catheter at the ostium. Cardiac pacing capture from the external cardiac stimulator will be obtained via connection to a diagnostic catheter. Once pacing capture is confirmed, ablation will be performed. Ablation dose will be selected at the investigator's discretion in accordance with LBL0198, FARASTAR Generator User Manual.

Ablation with the FARAWAVE Ablation Catheter may be repeated at the same site or at another target site at the physician's discretion using deployment configurations to suit target anatomy. Each addressable pulmonary vein will be ablated in turn beginning with placement of the guidewire, deployment of the ablation catheter, confirmation of pacing capture, and ablation. The effect of the ablation(s) may be checked post-procedure by pacing maneuvers, ECG recordings, 3D electroanatomic mapping, or by using the mapping electrodes on the ablation catheter splines.

Ablation using the FARAFLEX Ablation Catheter may be performed to close gaps in electrical isolation of pulmonary veins, focally ablate cardiac arrhythmias, or create a line of ablation at the cavo-tricuspid isthmus (CTI).

For a detailed description of procedure workflow refer to LBL0193 (FARADRIVE Deflectable Sheath), LBL0195 (FARAWAVE Endocardial AblationCatheter), LBL0565 (FARAFLEX Endocardial Ablation Catheter and LBL0198 (FARASTAR Endocardial Generator System).

3.11.2 75-Day Remap Procedure

The 75-Day Remap Procedure will follow the steps contained in **Section 3.11.1, Index Procedure**, as determined by investigator discretion to achieve protocol-required mapping and any required reablation.

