PLANNED PROCEDURE:	
Index Procedure:
 
Subjects will undergo an attempt to isolate all pulmonary veins or their anatomic equivalent.Subjects with a past history of atrial flutter, who are at risk of atrial flutter, who present with atrial flutter during the Index Procedure or who have inducible cavotricuspid isthmus-mediated (typical) flutter may undergo ablation of the cavo-tricuspid isthmus at the discretion of the investigator.Additional left atrial lesions may be made at the discretion of the investigator including focal sites, electrical gaps and lines of isolation. 
75-Day Remap Procedure:
 
Subjects will undergo a remapping procedure at 75 ± 15 days to assess the durability of the ablation lesions performed during the Index Procedure.During this procedure, additional ablations may be made at the discretion of the investigator to optimize patient outcomes.

PRIMARY SAFETY ENDPOINT:	
The primary safety endpoint for this study is the Composite Safety Endpoint (CSE) defined as the incidence of the following early-onset and late-onset serious adverse events (SAEs) which are device- or procedure-related, as adjudicated by the CEDMC. (See Table 4. Composite Safety Endpoint Definitions in Section 6.1).
 
Early onset (within 30 days of an Index or Remap Procedure)
 
• Death• Myocardial infarction (MI)• Persistent diaphragmatic paralysis• Stroke or transient ischemic attack (TIA)• Peripheral or organ thromboembolism• Pericarditis• Cardiac tamponade / perforation• Vascular access complications requiring intervention• Heart block 
Late onset (any time during follow-up through 12 months)
 
• Pulmonary vein (PV) stenosis (> 70% diameter reduction from baseline)• Atrio-esophageal fistula
SECONDARY SAFETY ENDPOINTS:	
1. The Primary Safety Endpoint assessed at 7 days2. The proportion of subjects with a device- or procedure-related SAE3. The proportion of subjects with stroke or TIA4. The proportion of subjects requiring cardioversion5. The proportion of subjects requiring an arrhythmia-related (AF, AFL or AT) hospitalization

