6.3 Primary Feasibility Endpoint

The proportion of subjects that achieve Acute Procedural Success (APS) defined as the percutaneous endocardial creation of a complete, electrically isolating set of lesions around the ostia of the pulmonary veins (PVI) using the FARAPULSE Endocardial Multi Ablation System during the Index Procedure, as clinically assessed by entrance and/or exit block performed \geq 20 minutes after the last PVI lesion is made.

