2.4.6.1. Primary Feasibility Analysis

The primary feasibility analysis is the proportion of subjects that achieve Acute Procedural Success (APS) defined as the percutaneous endocardial creation of a complete, electrically isolating set of lesions around the ostia of the pulmonary veins (PVI) using the FARAPULSE Endocardial Multi Ablation System during the Index Procedure, as clinically assessed by entrance and/or exit block performed \geq 20 minutes after the last PVI lesion is made.

CONFIDENTIEL / CONFIDENTIAL

Toute reproduction ou distribution, totale ou partielle, de ce document, sans autorisation préalable de ICON PLC est interdite.
Reproduction and distribution of this document, in whole or in part, is strictly forbidden without prior authorization from ICON PLC.

	STATISTICAL ANALYSIS PLAN	FARAPULSE PersAFOne SAP V1.0 PERSAFONE Page 17 /49
---	----------------------------------	--

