IF AF/AFL/AT status =0 **AND** DCCV90D=0 **AND** RF touch up=0 **AND** ABL>90 day=0 **AND** Class I/III AAD >90 days =1 in **MDT excel file** **THEN** Freedom from AF/AFL/AT, no DCCV>90 days, no RF, no ablation >90 days with Class I/III AAD >90 days='Yes'
ELSE Freedom from AF/AFL/AT, no DCCV>90 days, no RF, no ablation >90 days with Class I/III AAD >90 days='No'
- Derived criteria "Freedom from AF/AFL/AT, no DCCV>90 days, no RF, no ablation >90 days without Class I/III AAD >90 days" will be defined as follows:
IF AF/AFL/AT status =0 **AND** DCCV90D=0 **AND** RF touch up=0 **AND** ABL>90 day=0 **AND** Class I/III AAD >90 days =0 in **MDT excel file** **THEN** Freedom from AF/AFL/AT, no DCCV>90 days, no RF, no ablation >90 days without Class I/III AAD >90 days= 'Yes'
ELSE Freedom from AF/AFL/AT, no DCCV>90 days, no RF, no ablation >90 days without Class I/III AAD >90 days='No'
- Derived criteria "Freedom from AF, no DCCV>90 days, no RF, no ablation >90 days" will be defined as follows:
IF AF status =0 **AND** DCCV90D=0 **AND** RF touch up=0 **AND** ABL>90 day=0 in **MDT excel file** **THEN** Freedom from AF, no DCCV>90 days, no RF, no ablation >90 days ='Yes'
ELSE Freedom from AF, no DCCV>90 days, no RF, no ablation >90 days ='No'
- Derived criteria "Freedom from AF, no DCCV>90 days, no RF, no ablation >90 days with Class I/III AAD >90 days" will be defined as follows:
IF AF status =0 **AND** DCCV90D=0 **AND** RF touch up=0 **AND** ABL>90 day=0 **AND** Class I/III AAD >90 days =1 in **MDT excel file** **THEN** Freedom from AF, no DCCV>90 days, no RF, no ablation >90 days with Class I/III AAD >90 days ='Yes'
ELSE Freedom from AF, no DCCV>90 days, no RF, no ablation >90 days with Class I/III AAD >90 days ='No'
- Derived criteria "Freedom from AF, no DCCV>90 days, no RF, no ablation >90 days without Class I/III AAD >90 days" will be defined as follows:
IF AF status =0 **AND** DCCV90D=0 **AND** RF touch up=0 **AND** ABL>90 day=0 **AND** Class I/III AAD >90 days =0 in **MDT excel file** **THEN** Freedom from AF/AFL/AT, no DCCV>90 days, no RF, no ablation >90 days without Class I/III AAD >90 days='Yes'
ELSE Freedom from AF/AFL/AT, no DCCV>90 days, no RF, no ablation >90 days without Class I/III AAD >90 days= 'No'

Primary feasibility endpoint

IF Ablation with study device was successful = 'Yes' in **procedural form (PR)** **THEN** APS='Yes'

CONFIDENTIEL / CONFIDENTIAL

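### SAP 2.5 scores Acute Procedural Success from one yes/no form item and never checks that every pulmonary vein is isolated, so a subject with an untreated, still-conducting vein can count as a success

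*Protocol*

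**What the plan says.** Four places bear on which veins must be isolated.

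- **Protocol Executive Summary, Planned Procedure:** "Subjects will undergo an attempt to isolate all pulmonary veins or their anatomic equivalent".
- **Protocol 6.3:** APS needs a "complete, electrically isolating set of lesions around the ostia of the pulmonary veins (PVI"), made with the study system at the index procedure. Entrance and/or exit block is checked no sooner than "20 minutes after the last PVI lesion is made". SAP 2.4.6.1 repeats this definition in full.
- **Protocol 3.11.1:** "Each addressable pulmonary vein will be ablated in turn beginning with placement of the guidewire". The baseline electrical assessment carries the same limit, with FARAWAVE or a "commercially approved diagnostic catheter placed in each addressable pulmonary vein". Neither the protocol nor the SAP defines addressable.
- **SAP 2.5, Primary feasibility endpoint:** APS is Yes if "Ablation with study device was successful = 'Yes" on the procedural data form (PR), and No if that item is No. The rule uses no other field.

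The secondary endpoint in Protocol 6.4, Chronic Procedural Success (CPS), is expressly limited to veins that were initially ablated. APS carries no such limit.

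**The concern.** A vein that the catheter cannot reach or fit is something a device feasibility endpoint ought to register. Under the plain wording of Protocol 6.3, a vein left conducting means the isolating set is incomplete and APS is No. The SAP 2.5 rule does not compare veins isolated with veins present, and it does not use the 20-minute check. The SAP therefore contains a definition in 2.4.6.1 and a program in 2.5 that can give different answers for the same subject. No rule tells the investigator how an untreated vein should count. The result then rests on how each unblinded site reads one question, and Protocol 5.3 says the results will be used to design later studies.

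**Working it through.** The plan gives no target rate, power calculation or expected APS, so there is no figure to reproduce. The check sets the texts side by side, follows one hypothetical subject through them, and then illustrates the size.

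**1. Veins in scope**

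| Place | Veins covered | Basis |
|---|---|---|
| Protocol Executive Summary | all, or anatomic equivalent | attempt to isolate |
| Protocol 6.3, SAP 2.4.6.1 | the pulmonary veins, unqualified | isolation, block at 20 minutes or later |
| Protocol 3.11.1 | addressable (undefined) | baseline assessment and ablation |
| SAP 2.5, APS | none named | one item on success of study-device ablation |
| SAP 2.5, index vein counts | veins with isolated/blocked Yes or No | per-vein field on PR form |
| SAP 2.5, Durable PVI and veins with gaps | all six vein fields on remap form | no restriction to ablated veins |

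**2. One hypothetical subject.** Four veins are present, three are isolated, and the fourth is never approached and still conducts.

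- Protocol 6.3: APS = No.
- SAP 2.5: APS = Yes if the investigator answers for the ablation performed, and No if the investigator answers for all veins.
- Index vein proportion: 3/3 = 100% if the fourth vein is left blank, because it leaves numerator and denominator together. It is 3/4 = 75% if the field is completed as No.
- Remap, if the fourth vein is recorded there as not durable: Durable PVI = No and veins with gaps = 1. The proportion remaining isolated is (isolated at index − gaps)/isolated at index = (3 − 1)/3 = 67%, even if all three treated veins have held. The vein surfaces, but as a loss of durability rather than an acute failure.

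**3. The opposite error.** For CPS, SAP 2.5 cites an item on the same PR form asking whether all study-device ablation succeeded. If the APS item has that scope, a failed cavotricuspid isthmus (CTI) or posterior-wall lesion could make APS = No although every vein is isolated.

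**4. Size.** Inputs: N = 40 (Protocol 3.7 and 5.3) and N = 25 (shown only in SAP table shells 5 and 19). Number of affected subjects: not in the documents, so assumed to be 0, 1 or 2. One subject moves APS by 1/40 = 2.5 points or 1/25 = 4.0 points.

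Where asymptotic assumptions fail, SAP 2.1.4 uses Agresti-Coull at 100% and the exact interval otherwise. The SAP states no criterion; I assume they fail this close to 100%.

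- Agresti-Coull: ñ = n + z², p̃ = (x + z²/2)/ñ, lower limit = p̃ − z√[p̃(1 − p̃)/ñ], with z = 1.96. For 40/40, ñ = 43.84, p̃ = 0.9562, and the lower limit is 0.9562 − 0.0606 = 0.8956.
- Exact (Clopper-Pearson): lower limit = 0.025 quantile of Beta(x, n − x + 1).

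| Reclassified | N=40 | Lower 95% limit | N=25 | Lower 95% limit |
|---|---|---|---|---|
| 0 | 40/40 = 100% | 89.6% | 25/25 = 100% | 84.2% |
| 1 | 39/40 = 97.5% | 86.8% | 24/25 = 96.0% | 79.6% |
| 2 | 38/40 = 95.0% | 83.1% | 23/25 = 92.0% | 74.0% |

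The lower limit falls by about 3 to 6 points at N=40 and about 5 to 10 at N=25.

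If a share q of subjects has an untreated vein (assumption), the chance of at least one in 40 is 1 − (1 − q)^40: 33% at q = 1%, 64% at 2.5%, 87% at 5% and 98.5% at 10%.

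**The case against.** - **The form and its completion instructions are not supplied.** SAP 2.4.6.1 restates the full definition, so sites may be told to answer No when a vein is left conducting. The catheter instructions cited in Protocol 3.11.1 may also explain addressable. This stands: misclassification is possible, not shown.
- **An attempt on every vein is planned.** A vein attempted without isolation can be recorded as not isolated and stays in the index proportion. This stands for attempted veins, but the Executive Summary gives no scoring rule for a vein that was not attempted.
- **Independent review.** Protocol 5.2 and 9.10 send primary and major outcomes to the Clinical Events and Data Monitoring Committee, and SAP 2.1.2 lets committee-reviewed data prevail. The APS rule in SAP 2.5 nevertheless reads the PR form and names no adjudicated field.
- **A stronger reading is tempting:** that an unreachable vein disappears from the primary endpoint and from every vein-level result, so that feasibility is necessarily overstated. The documents do not support it. Durable PVI and veins with gaps have no ablated-vein filter, Protocol 3.12.5 remaps to assess isolation of the pulmonary veins without limiting this to treated ones, and a failed extra-vein lesion could pull APS down.

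**Conclusion.** The point holds in this limited form. The programmed rule for the primary feasibility endpoint does not implement its own definition: it omits which veins are present, isolation vein by vein, and the time of the block check. A subject with an untreated, conducting vein can therefore score APS = Yes, and if that vein is left blank it also leaves the index vein proportion. Whether this happens, and the net direction of error, cannot be settled from the documents.

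The size is 2.5 points of APS per affected subject at N=40, with the lower limit moving from 89.6% to 86.8% or 83.1% for one or two subjects. This assumes that all other subjects are true successes and that the asymptotic conditions in SAP 2.1.4 fail. The study is descriptive with no success threshold, so no test or decision rule changes. What is at stake is the estimate and its interval. The correction is worth making before the analysis is programmed.

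**What to change.** 1. In SAP 2.5, derive APS from the per-vein isolated/blocked fields on the PR form. Score Yes only if every pulmonary vein present, or its common or anomalous equivalent, is isolated with the study system at the check made 20 minutes or later. Count isolation from an adjacent lesion, because Protocol 6.3 turns on isolation and not on a separate application to each vein. Score No if any vein is not isolated, including veins not attempted.
2. Identify veins present from the baseline CT/MRI and the mapping already collected. The baseline catheter assessment alone will not serve, because Protocol 3.11.1 limits it to addressable veins.
3. Exclude CTI and other extra-vein lesions from APS.
4. Report the number of veins judged not addressable, with reasons, and show APS among addressable veins as a second row.
5. Reconcile the Executive Summary, Protocol 3.11.1 and Protocol 6.3 on which veins are in scope, and define addressable if it is kept. This concerns how the endpoint is scored; it does not say which veins should be treated.

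**Cost:** wording and programming, with no new procedure. Protocol 3.12.1 requires imaging for dimensions, so someone must list the veins per subject. The documents do not show whether the PR form records the time of the block check; if it does not, that must come from source records. APS may be slightly lower.

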3.11.3 Blanking Period

The Blanking Period consists of Day 0 (the date of Index Procedure) through and including Day 90.

During the Blanking Period, any recurrence of AF will be documented; however, recurrences of AF, AFL or AT during this time will not be considered Therapeutic Failures.

Subjects may undergo one repeat ablation during the Blanking Period without creating a Therapeutic Failure, following the procedure detailed in the preceding sections. This may occur during the Remap Procedure or at another procedure as clinically indicated.

If a second repeat ablation procedure is performed during this time, or any nonstudy device is used for cardiac ablation, the subjects will be considered a Therapeutic Failure but will remain in the study.

Towards the end of the Blanking Period, any AFD treatment will be discontinued unless the Investigator deems the withdrawal of AFD treatment not to be in the best interests of the patient.

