PRIMARY FEASIBILITY ENDPOINT:	The proportion of subjects that achieve Acute Procedural Success (APS) defined as the percutaneous endocardial creation of a complete, electrically isolating set of lesions around the ostia of the pulmonary veins (PVI) using the FARAPULSE Endocardial Multi Ablation System during the Index Procedure, as clinically assessed by entrance and/or exit block performed \geq 20 minutes after the last PVI lesion is made.

SECONDARY FEASIBILITY ENDPOINTS:	
1. The proportion of subjects who undergo the protocol-specified 75-Day Remapping Procedure and achieve Chronic Procedural Success (CPS) defined as persistent electrical isolation of all initially ablated pulmonary veins. Chronic Procedural Success will be subdivided by Index Procedure only CPS and Reablated CPS subjects.2. The proportion of attempted subjects that achieve Acute CTI Success, defined as the creation of bi-directional electrical block across the cavotricuspid isthmus using the investigational devices using the FARAPULSE Endocardial Multi Ablation System during the Index Procedure.3. Durability of the CTI and/or other extra-PV lesion set(s), when applicable. Durability is defined as unaltered integrity of each such lesion assessed at the Remapping Procedure.4. The proportion of subjects that achieve Therapeutic Success, defined as freedom from:
a. Post Blanking Period through assessment: occurrence of AF, AFL or AT or ablation for AF/AFL/AT using the study deviceb. At any time: ablation for AF/AFL/AT with a nonstudy device 
Therapeutic Success will be assessed from the end of the 90-day Blanking Period through Months 6 and 12 and will be subdivided by on / off AFDs (Atrial Fibrillation Drugs) post-Blanking Period.

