3.9 Duration of Subject Participation

Subjects will be followed at 30 days, 75 days, 6 months and 12 months with a 90-day Blanking Period for recurrent atrial fibrillation, atrial flutter or atrial tachycardia following the Index Procedure.

Reablation with the study device(s) during the Blanking Period is permitted but does not extend either the Blanking Period or the total follow-up interval.

The enrollment period is estimated to take 9 months and subjects will be followed for up to 12 months for a total duration of approximately 21 months.

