6.4 Secondary Feasibility Endpoints

1. The proportion of subjects who undergo the protocol-specified 75-Day Remapping Procedure and achieve Chronic Procedural Success (CPS) defined as persistent electrical isolation of all initially ablated pulmonary veins. Chronic Procedural Success will be subdivided by Index Procedure only CPS and Reablated CPS subjects.

2. The proportion of attempted subjects that achieve Acute CTI Success, defined as the creation of bi-directional electrical block across the CTI using the investigational devices.
3. Durability of the CTI and/or other extra-PV lesion set(s), when applicable. Durability is defined as unaltered integrity of each such lesion assessed at the Remapping Procedure.
4. The proportion of subjects that achieve Therapeutic Success, defined as freedom from:
 - a. Post-Blanking Period through assessment: occurrence of AF, AFL or AT, or ablation for AF/AFL/AT using the study device
 - b. At any time: ablation for AF/AFL/AT with a nonstudy deviceTherapeutic Success will be assessed from the end of the 90 Day Blanking Period through Months 6 and 12 and will be subdivided by on / off AFDs (Atrial Fibrillation Drugs) post-Blanking Period.

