2.4.6.2. Secondary Feasibility Analysis

The secondary feasibility analyses are:

- The proportion of subjects who undergo the protocol-specified 75-Day Remapping Procedure and achieve Chronic Procedural Success (CPS) defined as persistent electrical isolation of all initially ablated pulmonary veins. Chronic Procedural Success will be subdivided by Index Procedure only CPS and Reablated CPS subjects.
- The proportion of attempted subjects that achieve Acute CTI Success, defined as the creation of bi-directional electrical block across the CTI using the investigational devices.
- Durability of the CTI and/or other extra-PV lesion set(s), when applicable.
Durability is defined as unaltered integrity of each such lesion assessed at the Remapping Procedure.
- The proportion of subjects that achieve Therapeutic Success, defined as freedom from:
 - Post-Blanking Period through assessment: occurrence of AF, AFL or AT, or ablation for AF/AFL/AT using the study device
 - At any time: ablation for AF/AFL/AT with a non-study device
Therapeutic Success will be assessed from the end of the 90 Day Blanking Period through Months 6 and 12 and will be subdivided by on / off AADs (Atrial Fibrillation Drugs) post-Blanking Period.

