- Derived criteria "Durability of Left atrial roof line at remap" will be defined as follows:
IF Left atrial roof line lesion durable ='Yes' in **Follow-up 3D electroanatomical mapping form (RM)** **THEN** Durability of Left atrial roof line at remap = 'Yes'
ELSE IF Left atrial roof line lesion durable ='No' in **Follow-up 3D electroanatomical mapping form (RM)** **THEN** Durability of Left atrial roof line at remap = 'No'
- Derived criteria "Durability of Left atrial Posterior line" will be defined as follows:
IF Left atrial Posterior line lesion durable ='Yes' in **Follow-up 3D electroanatomical mapping form (RM)** **THEN** Durability of Left atrial Posterior line at remap = 'Yes'
ELSE IF Left atrial Posterior line lesion durable ='No' in **Follow-up 3D electroanatomical mapping form (RM)** **THEN** Durability of Left atrial Posterior line at remap = 'No'
- Derived criteria "Therapeutic Success ON/OFF AAD" will be defined as follows:

CONFIDENTIEL / CONFIDENTIAL

Toute reproduction ou distribution, totale ou partielle, de ce document, sans autorisation préalable de ICON PLC est interdite.
Reproduction and distribution of this document, in whole or in part, is strictly forbidden without prior authorization from ICON PLC.

IF "AF/AFL/AT status"= 0 **AND** "RF touchup"= 0 **AND** "ABL >90 days" = 0 **in MDT excel file**
THEN therapeutic success='Yes'
ELSE therapeutic success='No'

- Derived criteria "Therapeutic Success Off ADD" will be defined as follows:
IF Therapeutic success ='Yes' **AND** Class I/III AAD>90days=0 **in MDT excel file** **THEN** therapeutic success Off ADD ='YES'
ELSE IF Therapeutic success ='No' **AND** Class I/III AAD>90days=0 **in MDT excel file** **THEN** **THEN** therapeutic success Off ADD ='NO'
- Derived criteria "Therapeutic Success On ADD" will be defined as follows:
IF Therapeutic success ='Yes' **AND** Class I/III AAD>90days=1 **in MDT excel file** **THEN** therapeutic success On ADD ='No'
Else If Therapeutic success ='No' **AND** Class I/III AAD>90days=1 **in MDT excel file** **THEN** **THEN** therapeutic success On ADD ='No'

Additional endpoints

- Derived criteria "Proportion of all ablated pulmonary veins that are isolated at the Index Procedure using the study device" will be defined as follows:

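### Protocol 3.11.3 makes a second repeat ablation by Day 90 a Therapeutic Failure, but the Therapeutic Success definition and the SAP derivation score that subject as a success

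*Protocol*

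**What the plan says.** Protocol 3.11.3 fixes the window: "The Blanking Period consists of Day 0 (the date of Index Procedure) through and including Day 90". Inside it, "Subjects may undergo one repeat ablation during the Blanking Period without creating a Therapeutic Failure". That repeat may take place at the remap or at another clinically indicated procedure. The section then sets the limit, with Therapeutic Failure as the consequence, although the subject stays in the study. The sentence begins: "If a second repeat ablation procedure is performed during this time, or any nonstudy device is used for cardiac ablation, the subjects will be considered".

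Protocol 6.4 (secondary feasibility endpoint 4) defines Therapeutic Success as freedom from two things:

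- Limb (a), events after blanking only: "Post-Blanking Period through assessment: occurrence of AF, AFL or AT, or ablation for AF/AFL/AT using the study device"
- Limb (b), with no restriction in time: "At any time: ablation for AF/AFL/AT with a nonstudy device"

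The synopsis has the same two limbs. SAP 2.4.6.2 repeats them, with the second as "At any time: ablation for AF/AFL/AT with a non-study device". None of these texts mentions the number of repeat procedures during blanking. Protocol 3.9 adds: "Reablation with the study device(s) during the Blanking Period is permitted but does not extend either the Blanking Period or the total follow-up interval". It gives no number either.

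SAP 2.5 sets Therapeutic Success to Yes when AF/AFL/AT status is 0 and "RF touchup'= 0 AND 'ABL >90 days' = 0", all read from the MDT Excel file. The Databases part of SAP section 2.3 lists that file's fields. They include whether ablation was received at remap, whether it was RF or PFA, RF touchup, and ablation after Day 90.

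**The concern.** One section of the protocol calls a subject a failure, while the endpoint definition and the programmed rule call the same subject a success. The programmed answer is the favourable one, and it would be produced without anyone choosing it. Therapeutic Success is the study's measure of clinical benefit, and Protocol 5.3 says the results will inform the design of later studies. Time to Therapeutic Failure is also left open. SAP 2.4.7 and Table 11 list it, but SAP 2.5 gives no derivation, so nothing says whether or when a failure inside blanking is dated.

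**Working it through.** The plan states no sample size, expected rate or power for this endpoint, so there is no figure to reproduce. The check compares the rules and then sizes the effect of one subject.

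**Can the case arise?** Yes. The remap is at 75 ± 15 days, that is Day 60 to Day 90, so an on-schedule remap falls inside blanking. Protocol 3.12.5 lets the investigator close gaps there with study devices. A subject already re-ablated at a clinically indicated procedure can therefore have a second repeat by Day 90.

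**The rules as conditions.** Let R be the number of repeat ablations up to Day 90 (0, 1 or 2), S a nonstudy-device ablation at any time, A any AF/AFL/AT after blanking, and L any ablation after Day 90. S, A and L are each 0 or 1.

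- Protocol 3.11.3 together with 6.4: success if R ≤ 1, S = 0, A = 0 and L = 0.
- Protocol 6.4 alone: success if S = 0, A = 0 and L = 0.
- SAP 2.5: success if AF/AFL/AT status, RF touchup and ablation after Day 90 are all 0. For this comparison I assume that the status field codes A and that RF touchup codes S. The SAP defines neither.

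**Comparison.** There are 3 × 2 × 2 × 2 = 24 combinations. The three rules agree in 23 and differ in one:

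| R | S | A | L | 3.11.3 with 6.4 | 6.4 alone | SAP 2.5 |
|---|---|---|---|---|---|---|
| 1 | 0 | 0 | 0 | success | success | success |
| 2 | 0 | 0 | 0 | **failure** | **success** | **success** |
| 2 | 0 | 1 | 0 | failure | failure | failure |
| 2 | 1 | 0 | 0 | failure | failure | failure |

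The first row is the permitted single repeat. The last two show that a twice-repeated subject who recurs later, or who has nonstudy ablation, fails under every rule. Only the second row is in dispute.

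**Can the named file separate the first two rows?** No. A subject whose only repeat was at the remap and a subject also re-ablated earlier carry the same remap flags. There is no field for a study-device ablation between the index procedure and the remap, and no count of repeats.

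**Size.** One subject is 1/40 = 2.5 percentage points at the planned maximum of 40. With a smaller denominator it is 1/n. The documents give no expected success rate, so these counts are assumptions (exact Clopper-Pearson 95% intervals):

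| Assumed successes under SAP rule | Disputed subjects re-scored | Rate | 95% interval |
|---|---|---|---|
| 28/40 | 0 | 70.0% | 53.5 to 83.4 |
| 28/40 | 1 (27/40) | 67.5% | 50.9 to 81.4 |
| 28/40 | 2 (26/40) | 65.0% | 48.3 to 79.4 |

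The step is the same from other starting rates: 24/40 = 60.0% becomes 57.5%, and 32/40 = 80.0% becomes 77.5%.

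**The case against.** **The sections may be complementary.** Section 3.11.3 could be read as adding to 6.4, so that the protocol has one combined rule. That removes the conflict within the protocol, but not the one with the SAP. SAP 2.4.6.2 and 2.5 lack the clause, and the file cannot supply it.

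**The other rule may be the intended one.** The synopsis, 6.4 and SAP 2.4.6.2 all omit the limit, and 3.9 permits study-device reablation without a number. This stands in part: the documents do not say which text prevails. Section 3.11.3 is, however, the only one that addresses a second repeat expressly.

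**The consequence is small.** The endpoint is one of four secondary feasibility endpoints, reported without a hypothesis test. The conflict needs one specific history, which may never occur. This stands and limits the severity.

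**The SAP follows an older protocol.** It cites Revision C, while the protocol supplied is Revision E. Whether Revision C had the clause cannot be checked, so a reader should not infer that the SAP departed from its own parent version. The inconsistency inside Revision E does not depend on this.

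**RF touchup may already mean any nonstudy-device ablation.** A reader might infer that the SAP scores a non-RF, nonstudy ablation by Day 90 as a success. That follows only if the field is coded literally, and the coding is not given. What stands is that the SAP must define it.

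**Conclusion.** The inconsistency is real but narrow. It affects only subjects with two or more study-device repeats by Day 90 and no other failure criterion. For them the SAP gives success where 3.11.3 gives failure. Each one moves the rate by 2.5 points at N = 40, always towards success. This assumes that AF/AFL/AT status records arrhythmia recurrence, as its name suggests, and not the second-repeat rule. No primary endpoint, test or sample size changes. I rate it moderate.

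Some stronger readings are not supported:

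- *An expected number of affected subjects.* Protocol 1.3 reports rehospitalisation for atrial arrhythmia in 3 of 40 and 3 of 60 earlier patients, which might be used as a proxy. It does not say that any of these was treated by ablation or fell within 90 days. Protocol 4.3 describes earlier patients as treated for paroxysmal AF. Such a product would also leave out the condition that the subject stays free of arrhythmia afterwards.
- *A 4-point effect at N = 25.* That N is printed in SAP Tables 5 and 19. Therapeutic Success is in Table 13, where N is blank.
- *An event removed from Time to Therapeutic Failure.* There is no programmed derivation from which to remove one. The gap is the missing derivation.
- *That these are the poorest responders.* Remap ablation is at the investigator's discretion, so a second repeat need not reflect recurrence.

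**What to change.** Reconcile 3.11.3 with the synopsis, 6.4 and the SAP. Following the only text that covers the case, the changes would be:

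1. Add a third limb to Therapeutic Success in the synopsis, Protocol 6.4 and SAP 2.4.6.2: more than one repeat ablation procedure by Day 90.
2. In SAP 2.5, derive a dated count of repeat ablation procedures up to Day 90 from the CRF, not from the MDT file. The inputs exist: ablations since the last visit (Protocol 3.12), the remap form, and the data behind SAP Listing 12.
3. Set Therapeutic Success to No when the count is 2 or more.
4. Add a derivation of Time to Therapeutic Failure to SAP 2.5, dating this failure at the second repeat.
5. State in SAP 2.5 that RF touchup means any nonstudy-device ablation for AF/AFL/AT at any time, as limb (b) of 6.4 requires.

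If the sponsor intends 6.4 to prevail, it should amend 3.11.3 instead; items 4 and 5 are still needed, with item 4 dated by the rule that remains.

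The cost is one line in each definition, one derived count, one time-to-event derivation and one field definition, with no new data collection. The reported success rate may become slightly less favourable.
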